ADDITION TREATMENT OUTCOME MONITORING STUDY

PROTOCOL AND STATISTICAL ANALYSIS PLAN

[name]

Last modified October 14, 2019

MEASURE SCHEDULE

Instrument	Abbrev.	Screen	Baseline	Week 6	Week 12	Week 26
Alcohol Use Disorder Identification Test – Consumption Version	AUDITC	x				
Eligibility criteria, self-report	ELIG	x				
Eligibility criteria, HER	ELIG_EHR	x				
Follow-up cover sheet	FUP		x	x	x	x
Contact information	CONTACT	x	x	x	x	x
Demographics	DEMO		x			
Technology use	TECH		x			
Substances focused on in treatment	SUBSTANCE S		x			
Treatment Goal	TXGOAL		x			
Short Inventory of Problems (Lifetime)	SIPL		x			
Weekly check-in (if not completed remotely)	CHECKIN		x	x	x	x
ASI-LITE (alcohol and drug consumption past 30 days)	ASILITE		x	x	x	x
AUD checklist	AUDCHK		x	x	x	x
SUD checklist	SUDCHK		x	x	x	x
Brief Situational Confidence Questionnaire	SEQ_SUBST ANCE		x	x	x	x
Readiness Rulers	RR		x	x	x	x
Penn Alcohol Craving Scale	PACS		x	x	x	x
PHQ-9	PHQ9		x	x	x	x
Service use	SERVICES		x	x	x	x
Usability of check-in survey	USA_SURVE Y		x	x	x	x
Self-efficacy for check-in survey	SEQ_SURVE Y		x	x	x	x
Working alliance inventory, short form	WAISF		x	x ¹	x ¹	x ¹
Treatment satisfaction	TXSATIS		x	x ¹	x ¹	x ¹
In-session discussion survey	INSESS		x	x ¹	x ¹	x ¹
Audio recording of sessions (if opted in)	AUDIOCONS ENT			x		
Qualitative experiences using ATOM tool	ATOM_EXP			x	x	x
Qualitative experiences being in the study	STUDY_EXP				x	x
EHR measures (completed by RA)	EHR					x
Demographics, clinicians	DEMO_CL		x			
In-session discussion survey, clinicians	INSESS_CL			x ¹		
Dashboard usability, clinicians	USA_CL				x	

White background = complete by patients. Gray background = completed by clinician

¹ = Completed only if the patient has attended treatment at HMHAS since the last completed assessment.

STUDY FLOW - CLINICIANS

Recruitment (clinicians)

- **Clinician** participants will be recruited through verbal announcements at staff meetings and by placing letters inviting them to participate in clinicians' mailboxes.
- The research team will make efforts to recruit clinicians prior to recruiting patients.

Screening and Eligibility (clinicians)

- Eligibility will be extended to all clinicians who are employed within the Addictions Clinic or who are identified as harm reduction therapists for patients with substance use disorders within the Harborview Mental Health and Addictions Services (HMHAS) clinic.

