- Eligibility criteria will be confirmed by research staff in a private area, typically in the clinician's office or in our research office (which is in the same building as the clinic).
- When a clinician enrolls, they will complete a demographics questionnaire and be informed about the procedures that some of their patients may experience if they enroll in the study.
- We will ask if the clinician wishes to opt-in to audio recording one treatment session with any of their patients who will enroll in the study. Clinicians will be told they can opt out at any time, and that these audio recordings will only be allowed if both the clinician and patient opt-in to audio recording.
- We will offer clinicians brief training on how to use an online dashboard that presents the results of the weekly "check-in" survey that some of their patients may complete in this study.

When a clinician is the primary counselor for a patient who is enrolled in the study:

- If the clinician's patient is in the **green group**, the clinician will receive an information-only email from the study staff notifying them that their patient is in the study and that their weekly check-in results WILL be available for review.
- If the patient is in the **blue group**, the clinician will receive an information-only email from the study staff notifying them that their patient is in the study but their weekly check-in results WILL NOT be available for review.
- For patients in either group, the email will also notify the clinician that we will ask them to complete brief, questionnaires at 6 and 12 weeks, described below.

Brief questionnaire at 6 weeks after a patient enrolls in the study:

- Clinicians will be emailed a REDCap survey invitation. The survey will ask them to describe how much their most recent treatment session with the identified patient was focused on the each of the topics that are measured by the weekly check-in.
- If the patient and clinician both opted-in for audio recordings, research staff will work with the clinician to facilitate audio recording of a one-to-one counseling session near the six-week time point.

Brief questionnaire at 12 weeks after the patient enrolls in the study (green group only**):**

- Clinicians will be emailed a REDCap survey survey invitation. The survey will ask them to rate the usability of the dashboard used for reviewing patient progress with their patient.

Notification at 24 weeks (green group only**):**

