- Clinicians will be notified via email that their patient has completed the study. The patient will no longer be able to complete weekly check-ins; however, the check-ins they have completed will remain available for clinicians to see for as long as the study is active.

End of study (after clinician's patients have all completed the study)

- Clinicians will be invited to complete a 30-minute qualitative interview with a member of the study team, focusing on providing open-ended feedback about the dashboard (e.g., what they liked about it, what they didn't like about it, what we could do to improve it).

STUDY FLOW - PATIENTS

Recruitment

- **Patient** participants will be recruited through flyers and handouts placed in the clinic (e.g., at check-in desk, in the waiting area, information desk).

Screening

- Patients who are interested in participating will typically be screened via telephone; however, they may occasionally be screened in person in a private research office in the same building as the HMHAS clinic if the patient prefers an in-person screening. Research staff will work to ensure adequate privacy (e.g., conducting screening in research office, asking patients if they are in an area with enough privacy to discuss sensitive questions during telephone interviews).
- During the screening, an RA will provide a brief overview of the study, including that the study duration is up to 6 months long and that participation is completely voluntary.

Eligibility criteria will be assessed in the screening process. Criteria include:

- At least 18 years old.
- Self-reports that they are a patient at HMHAS clinic.
- Self-reports that they are receiving services at HMHAS clinic for an alcohol or drug-related concern.
- Has a smartphone with a working phone number and a mobile plan that allows text messages and internet connection.
- AUDIT-C score indicates past-year hazardous drinking (summed score is at least 3 or 4 for women or men, respectively), or self-reports any drug use for non-medical reasons in the past year.
- Does not anticipate moving away from Seattle within 6 months.
- Does not anticipate becoming incarcerated in next 6 months.
- Able to speak and read English (based on self-report).

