 - Prior to the patient's scheduled counseling session, research staff will give their clinician an envelope with a consent form allowing for permission to audio record, (the form will use large, bold font to indicate that both the patient and clinician must both agree to recording on the date that the recording is made and must sign the form prior to the recording). The envelope will also include a digital audio recorder (with any pre-recorded audio wiped from the device) along with instructions on how to use the recorder. Clinicians will be asked to keep these materials in a drawer or cabinet in their office, which per clinic policy must remain locked at all times.
 - Within 2 business days of the completed session, the research staff will retrieve these materials from the clinician. Signed consent forms will be filed and audio recordings will be removed from the recording devices.

EHR Coding – 6 months after baseline

- Research staff will review patients' UW/Harborview electronic health records (via EPIC) for the six-month period after the participant enrolls. EHR data will never be printed or downloaded; it will only be coded using research forms. Direct identifiers will not be recorded on research forms. Research staff will use EHR coding forms to obtain the study information and will then enter information from these forms into REDCap.

DATA ANALYSIS PLAN

- Descriptive statistics, data visualizations, and multilevel models will be used to characterize measures of acceptability and engagement with the intervention with 95% CI's. Statistics on enrollment (e.g., number of patients and clinicians eligible and willing to participate), measure completion, and dashboard use will be used to assess acceptability and engagement.
- Linear regression models will compare participants in the measurement-only (blue group) vs. measurement and feedback (green group) conditions on in-session discussion topics.
- Multilevel models will generate effect size estimates and 95% CIs to examine whether TABLET sessions have differential degrees of changes in weekly progress and measures. Models will be two-level (repeated measures nested within patients); however, the need for three-level models (patients nested within clinicians) will be tested. Fixed effects for study condition and fixed effects for time will be used to generate growth curve models of change over time in each

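### The in-session discussion comparison states no baseline adjustment, although assignment is non-random by enrolment order and patient-reported discussion is measured at baseline

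*Combined protocol and SAP*

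**What the plan says.** The second bullet of the Data Analysis Plan reads: "Linear regression models will compare participants in the measurement-only (blue group) vs. measurement and feedback (green group) conditions on in-session discussion topics". That is all the plan says on this comparison. It names no covariate, no week, and neither of the two possible reporters (patient or clinician).

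Three other places bear on it.

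- **Condition Assignment.** Allocation is declared non-random. The first 20 patients to enter are blue and the rest green. If fewer than 20 have enrolled by the sixth month of recruitment, later patients go to the two groups in balanced order, which is not random either.
- **Measure Schedule.** "In-session discussion survey" appears twice. The patient version (INSESS) is marked at baseline and at weeks 6, 12 and 26. The clinician version (INSESS_CL) is marked at week 6 only. The follow-up entries carry the footnote "Completed only if the patient has attended treatment at HMHAS since the last completed assessment"; the baseline entry does not.
- **Data Analysis Plan, third bullet.** For the growth models, "the need for three-level models (patients nested within clinicians) will be tested". Nothing similar is said for the linear regression.

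**The concern.** The two groups differ by design only in whether the clinician sees the weekly check-in results. What is discussed in session is the measured outcome closest to that difference, although the plan does not rank its outcomes.

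With allocation by enrolment order, randomisation cannot be relied on to balance the groups. The first patients to join may already differ from later ones in how much their sessions cover the check-in topics. A regression on condition alone would attribute such a difference to feedback, in whichever direction it fell. A baseline measure of the same construct from the same reporter is already scheduled, and the plan does not say that it will be used.

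**Working it through.** **Inputs.** The documents supply 20 blue patients under the default rule. They give no total N, SD, correlation, reliability or effect size, so there is no planned figure to reproduce. The following are assumptions: 20 green patients, outcome SD 1, no true effect, correlation r between true baseline level and follow-up of 0.2 to 0.6, baseline imbalance D of 0 to 0.5 SD, and reliability of the baseline score 0.8 unless stated.

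**1. Regression on condition only.** Bias = r × D. The standard error is √(1/20 + 1/20) = 0.316, and with t(38) = 2.024 the 95% half-width is 2.024 × 0.316 = 0.64 SD. Coverage follows from the non-central t distribution with non-centrality bias/0.316; simulation with 20,000 runs agrees.

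| D | r | Bias (SD) | Coverage |
|---|---|---|---|
| 0 | any | 0 | 95% |
| 0.25 | 0.5 | 0.125 | 93% |
| 0.5 | 0.2 | 0.10 | 94% |
| 0.5 | 0.3 | 0.15 | 92.5% |
| 0.5 | 0.5 | 0.25 | 88% |
| 0.5 | 0.6 | 0.30 | 84% |

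For D = 0.5 and r = 0.5, 88% coverage means that about 12% of tests would reject a true null. With 10, 30 or 40 green patients, coverage in that case is 90%, 86.5% and 85%.

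**2. Regression on condition and baseline score.** Measurement error in the baseline score leaves a residual bias of r × D × (1 − reliability). For D = 0.5 and r = 0.5:

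- reliability 0.8: 0.25 × 0.2 = 0.05 SD, coverage 95%;
- reliability 0.5: 0.25 × 0.5 = 0.125 SD (0.12 in simulation), coverage 93%.

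So adjustment removes most of the bias when the score is reliable and half of it at reliability 0.5.

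**3. Effect on precision (reliability 0.8, simulated).** With no imbalance the interval is 9% narrower at r = 0.5 and unchanged at r = 0.2. With D = 0.5 it is 7% narrower at r = 0.5, unchanged at r = 0.3 and 2% wider at r = 0.2.

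**4. Disclosure before baseline.** Patients learn their group during consent and complete the remaining baseline measures afterwards. Suppose that this knowledge shifts green baseline reports by s. The slope on the observed score is r × reliability = 0.5 × 0.8 = 0.4, so adjustment adds −0.4 × s.

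- No true imbalance: s = 0.2 gives −0.08 SD; s = 0.5 gives −0.20 SD (coverage about 90%).
- D = 0.5: s = +0.2 gives 0.25 − 0.4 × 0.7 = −0.03 SD; s = −0.2 gives 0.25 − 0.4 × 0.3 = 0.13 SD. Both are smaller in size than the unadjusted 0.25 SD.

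**The case against.** **Silence is not a decision.** The analysis plan is three bullets long, and linear regression can carry a covariate. A reader might infer that the sponsor has ruled out baseline adjustment; the text does not say that. What stands is that none is stated, so in a non-randomised comparison the choice could be made after the results are seen.

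**The harm is assumed.** Nothing in the documents shows an imbalance or gives a correlation. The correlation may be low: the clinician survey asks clinicians to "describe how much their most recent treatment session with the identified patient was focused on" each topic, and if the patient version also refers to a single session, topics may vary from one to the next. This stands, and is why the size is given as a range starting at zero.

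**The covariate is imperfect.** Baseline INSESS is answered after the group is known. Eligibility also accepts appointments that are only scheduled, so some patients may have no session to rate at baseline. Both points stand. They argue for showing two estimates rather than for omitting the adjustment.

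**Shared clinicians.** Clinicians are expected to have several study patients: they may agree to "audio recording one treatment session with any of their patients who will enroll in the study", and their final interview waits until their "patients have all completed the study". A reader might infer that ignoring this inflates false positives. The documents do not support that, because the direction depends on how each clinician's patients divide between groups. Since "The research team will make efforts to recruit clinicians prior to recruiting patients", clinicians with patients in both groups are plausible. In simulations with 8 clinicians and an intraclass correlation of 0.3, plain regression covers 97% if clinicians are balanced across groups, 95% if randomly spread, and 92% to 89% if 80/20 drift occurs. Cluster-robust intervals are 2% to 44% wider in those settings, and 54% to 120% wider with 4 clinicians. The remedy could cost more than the problem.

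**Attendance.** Follow-up INSESS exists only for attenders, which could also bias the contrast. Baseline adjustment is not aimed at that, and it adds nothing to the size of this point.

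**Conclusion.** The point holds for baseline adjustment. The plan compares non-randomly formed groups, will hold a baseline score of the same construct, and does not state that it will use it. With 20 per group and r = 0.5, an imbalance of 0.25 to 0.5 SD would bias the unadjusted estimate by 0.125 to 0.25 SD and lower coverage to 93% to 88%. With no imbalance there is no harm. Every input except the 20 blue patients is assumed.

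Two stronger conclusions do not follow. The comparison cannot be called biased, since no imbalance is shown. Nor would adjustment make it unconfounded: calendar time stays tied to group under the default rule, measurement error leaves part of any imbalance, and answers given after disclosure can introduce bias. This is an inexpensive improvement to the main estimate of this comparison; it does not rescue or invalidate the design.

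**What to change.** Replace the second bullet with:

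> For each topic, patient-reported INSESS at week 6 will be compared by linear regression on condition and baseline INSESS; the estimate without baseline adjustment will be shown beside it. Week-6 INSESS_CL, which has no baseline, will be compared between conditions separately, without baseline adjustment.

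Week 6 is proposed because it is the only week with both reports. Give the number of patients behind each estimate, since a few may lack a baseline score.

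State two limitations: baseline INSESS is answered after the condition is known, and calendar time remains confounded with group. Tabulate patients per clinician by group. A clinician term or cluster-robust variance can be an optional sensitivity analysis, because its benefit depends on the unknown number and spread of clinicians.

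**Cost.** Wording only; no new data or visits. On the assumptions above, the interval ranges from 9% narrower (r = 0.5, no imbalance) to about 2% wider (r = 0.2, 0.5 SD imbalance). The real downside is the bias added if disclosure altered baseline reports: 0.08 SD for a 0.2 SD shift with no true imbalance, more for a larger shift. Showing both estimates lets the reader see how far the adjustment moves the result.

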TABLET-recorded measure. Growth-curve modeling will allow testing between conditions in the amount of change over time for each construct.

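### Patients rate in-session discussion at up to three follow-ups, but the planned linear regression names no rater, visit or handling of repeats, and the two-level models are not extended to it

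*Combined protocol and SAP*

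**What the plan says.** The second bullet of the Data Analysis Plan reads: "Linear regression models will compare participants in the measurement-only (blue group) vs. measurement and feedback (green group) conditions on in-session discussion topics". It gives no rater, time point, summary over visits, baseline adjustment or variance estimator.

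The Measure Schedule holds two instruments that could supply this outcome:

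- The patient form, "In-session discussion survey" (INSESS), is marked at baseline and at three follow-ups. Each follow-up mark carries footnote 1: "Completed only if the patient has attended treatment at HMHAS since the last completed assessment".
- The clinician form, "In-session discussion survey, clinicians" (INSESS_CL), is marked at week 6 only. The clinician study flow describes it: "The survey will ask them to describe how much their most recent treatment session with the identified patient was focused on" each check-in topic.

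The third bullet of the Data Analysis Plan specifies multilevel models: "Models will be two-level (repeated measures nested within patients); however, the need for three-level models (patients nested within clinicians) will be tested". It ties them to weekly progress and to each TABLET-recorded measure, a term the document does not define, and closes: "Growth-curve modeling will allow testing between conditions in the amount of change over time for each construct". It does not say whether INSESS is one of these measures.

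**The concern.** Under Condition Assignment, the groups differ only in whether clinicians see the check-in results. What is discussed in sessions is therefore arguably the outcome closest to the intervention, yet its model is the least specified. The plan recognises repeated measures in the third bullet but does not carry that structure over to an outcome that patients rate repeatedly by design.

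Two losses are possible, depending on how the second bullet is carried out. A regression at one visit sets aside the other follow-up ratings and excludes any patient who lacks that visit's rating, even when others exist. Such gaps are to be expected: footnote 1 makes each follow-up rating conditional on attendance, and the Assessments section lets patients stay in the study after leaving treatment. A regression that stacks all visits as independent rows would instead give intervals that are too narrow. With 20 patients planned for the blue group, precision is scarce. While rater, visit and handling remain open, they can also be chosen after the data are seen.

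**Working it through.** The document gives no power calculation, standard deviation, within-patient correlation or expected attendance, so there is no figure to reproduce. The correlations (ρ), attendance rates and green-group sizes below are assumptions.

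**Inputs from the document**

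- Patient ratings: one at baseline and up to three afterwards (Measure Schedule). The schedule puts the last follow-up at week 26 and the Assessments section at 24 weeks. These should be reconciled, but the count of three is the same in both.
- Clinician ratings: one per patient, at week 6.
- Group sizes: the first 20 patients to blue and the rest to green, with a different rule if recruitment is slow (Condition Assignment). No green or total number is given.

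**One visit against all three.** For three equally correlated ratings per patient, the standard error from one visit divided by that from the mean of three is √(3/(1+2ρ)).

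**Three visits pooled as independent rows.** The design effect is 1+2ρ, and the true coverage of a nominal 95% interval is 2Φ(1.96/√(1+2ρ)) − 1.

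| ρ (assumed) | 1+2ρ | SE, one visit / all three | Coverage if pooled as independent |
|---|---|---|---|
| 0.1 | 1.2 | 1.58 | 0.926 |
| 0.3 | 1.6 | 1.37 | 0.879 |
| 0.5 | 2.0 | 1.22 | 0.834 |
| 0.7 | 2.4 | 1.12 | 0.794 |

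A simulation (20,000 runs, 20 against 20 patients, three ratings each) gave pooled coverage of 0.875, 0.827 and 0.784 at ρ = 0.3, 0.5 and 0.7.

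**Scale of the precision gain.** With 20 blue and an assumed 20 green, the 95% half-width at one visit is 1.96 × √(1/20 + 1/20) = 0.62 SD. Multiplying by √((1+2ρ)/3) gives 0.45, 0.51 and 0.55 SD at ρ = 0.3, 0.5 and 0.7. With 10 or 40 green patients the one-visit half-width is 0.76 or 0.54 SD.

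**Incomplete attendance.** For patients with two follow-up ratings, one of them at the chosen visit, the ratio becomes √(2/(1+ρ)) = 1.24, 1.15 and 1.08, so the gain shrinks. The share of follow-up ratings left unused by a week-6 regression also depends on attendance at the three follow-ups:

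- 100/100/100%: 1 − 1/3 = 67%
- 90/70/50%: 1 − 0.9/2.1 = 57%
- 90/50/20%: 1 − 0.9/1.6 = 44%

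**Regression on each patient's mean follow-up rating.** With three ratings each, simulated coverage was 0.948 to 0.949, and no rating is lost. When the number of ratings varies, an unweighted regression treats all means as equally precise. The variance of a single rating is 3/(1+2ρ) = 1.88, 1.50 and 1.25 times that of a mean of three at ρ = 0.3, 0.5 and 0.7. A mixed model takes this into account.

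**Clinician rating.** There is one value per patient, so neither loss arises from repeated ratings. Patients who share a clinician may still be correlated.

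**The case against.** A reader might infer that linear regression forces a choice between discarding two thirds of the ratings and reporting intervals that are too narrow. The document does not support that. Regression on patient means uses every rating with sound coverage, and separate regressions at each visit also use every rating, though they give three results with no stated summary. The bullet speaks of models in the plural and does not say that they are ordinary least squares on stacked rows. Two thirds also assumes that every patient attends before every follow-up.

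Pooling rows as independent is the least supported reading. The bullet compares participants, which suggests one value each, and the next bullet shows that the authors recognise nesting. The bullet itself promises no 95% interval; only the first and third do. The coverage figures therefore describe a risk to be closed off, not a planned analysis.

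The bullet may also mean the clinician's rating, which exists once per patient and is the only in-session survey described in the study-flow text. Linear regression would then raise no repeated-measures problem. Conversely, if INSESS counts as a TABLET-recorded measure, the third bullet might already cover it. Both readings are open, and neither says how the patient ratings enter the comparison in the second bullet.

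Finally, a week-6 difference and an average over follow-ups are different quantities. Staff outreach on check-ins stops after three months, and later ratings come only from patients still attending. This stands: the average should not replace the week-6 result, and its population must be stated.

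**Conclusion.** The concern holds in a limited form. Patients rate in-session discussion repeatedly, the planned comparison names only linear regression, and nothing extends the two-level models to it. A joint model of the patient ratings is a better method than a single-visit regression, and its model class is already in the plan.

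With complete ratings and assumed ρ of 0.3, 0.5 or 0.7, a single-visit analysis has a standard error 37%, 22% or 12% larger than one using all three follow-ups. The gain is smaller when patients have fewer ratings. The fall in coverage to about 88%, 83% or 79% applies only if rows were pooled as independent, and at ρ = 0.1 it would be slight (93%). The documents do not show that either loss will occur. They leave the choice open, and they do not establish about 20 patients per group, since only the blue target is stated.

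**What to change.** Amend the second bullet to name the rater and the model for each form.

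- **Patient rating (INSESS).** Fit a two-level model to all available follow-up ratings within patients, with fixed effects for condition, visit and condition-by-visit. Adjust for the baseline INSESS rating, because assignment is non-random. Apply the test for a clinician level that the third bullet already plans. Report the average post-baseline green-minus-blue difference with its 95% CI, and the difference at each visit, including week 6. State that later ratings exist only for patients still attending.
- **Clinician rating (INSESS_CL).** Keep linear regression for the single week-6 value, and allow for patients who share a clinician.

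The cost is a few sentences of plan wording and slightly more analysis work, with no new data collection. The downside is that the average must be interpreted among patients still in treatment. Baseline adjustment does not remove all confounding from non-random assignment.
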